## **7.2 Baseline Visit (may be performed up to 3 weeks prior to 1st vaccination)**

Baseline evaluations determine if the patient is an eligible candidate for study participation and establish the patient's health status at the time of study entry. Standard-of-care laboratory evaluations done prior to signing consent will qualify for baseline evaluations if they have been conducted within 90 days prior to enrollment. Standard-of-care MUGA or ECHO done prior to signing consent will qualify for baseline evaluations if conducted within 90 days prior to enrollment. All baseline evaluations must be completed before study agent is dispensed. If a study patient is found to be ineligible any blood collected for research purposes will be destroyed. The destruction of the blood will be clearly documented in the documented study records.

- 7.2.1. Sign informed consent prior to any study-specific baseline testing
- 7.2.2. Medical history and complete physical examination which includes weight, vital signs, baseline symptom assessment, review of concomitant medications, and ECOG scoring (Appendix A)
- 7.2.3. MUGA or ECHO
  - a. LVEF must be  $\geq$ LLN per institution performing the test, to allow the patient to continue with vaccination
- 7.2.4. Patients will have the following tests and procedures completed prior to the first vaccine.
  - a. Clinical labs
    - i. Complete blood count (CBC) with WBC differential, hemoglobin and platelet count
    - ii. Comprehensive metabolic panel (CMP) which includes electrolytes, glucose, creatinine, blood urea nitrogen (BUN), AST (SGOT), ALT, alkaline phosphatase, and total bilirubin
    - iii. HbA1c
- 7.2.5. Urine pregnancy testing will be performed on female patients who are having sex that could lead to pregnancy. If a patient is found to be pregnant, she will not be able to participate in the study.

## **7.3 First Vaccination**

- 7.3.1. Patients will have the following tests and procedures completed prior to the first vaccine:
  - a. Vital signs
  - b. Complete blood count (CBC) with WBC differential, hemoglobin and platelet count if not completed within 90 days of enrollment

- c. Comprehensive metabolic panel (CMP) which includes electrolytes, glucose, creatinine, blood urea nitrogen (BUN), AST (SGOT), ALT, alkaline phosphatase, and total bilirubin (within 2 days of visit is allowable)
  - i. Review non-fasting glucose value prior to vaccine administration then follow Section 8.5.1.1 to determine whether vaccine can be administered
- d. ANA, anti-ds DNA, C3, TSH
- e. GAD65
- f. Urine pregnancy testing if applicable

7.3.2. Approximately 200 ml of blood (about 1 cup) will be collected for immunologic monitoring, prior to the first vaccine. It is possible that this volume of blood loss could cause the patient to feel lightheaded or dizzy. If clinically indicated, IV fluids will be administered

7.3.3. Tetanus diphtheria (Td) immunization if one has not been administered within six months and used as a positive control for immune responses. If patient has a history of an allergic reaction to the Td immunization, one will not be given and patient can still continue to be in the study as there are other positive controls used for immune assays.

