#### First Vaccination Visit:

Clinical labs, immune monitoring labs, research blood for immunologic monitoring, Tetanus diphtheria (Td) vaccination (if applicable), and intradermal (id) vaccination with assigned dose

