### **3. SUMMARY OF STUDY PLAN**

This will be a Phase I, non-randomized, dose escalation study in patients with node positive non-metastatic HER2 negative breast cancer that are in remission and defined as no evidence of disease (NED). The study will accrue 30 evaluable patients with up to 12 patients in each dose arm.

Patients will be assigned sequentially to one of three arms defined by vaccine dose. Patients will be accrued to Arm 1 first, then Arm 2, then Arm 3. Each dose arm will have a staggered enrollment. There will be one week between the first patient's vaccination 1 visit and second patient's vaccination 1 visit to each dose arm to ensure no toxicities. Furthermore, three patients will initially be enrolled to a dose arm, receive the first vaccine, and be evaluated for toxicity prior to the second vaccine (1 month of monitoring) before the remaining patients will be enrolled in that dose arm.

If there is sufficient evidence (please refer to Section 8.5.1“Accrual and Criterion for Premature Study termination”.) to suggest the Arm 1 dose is safe (Section 13.1), then the Arm 2 cohort of up to 12 patients will be enrolled. If the Arm 2 dose is also sufficiently safe then enrollment into the Arm 3 dose may move forward. If the Arm 3 dose appears safe, the immunologic efficacy among three dose groups will be examined to determine the recommended phase 2 vaccine dose for further cancer prevention studies. Immunologic efficacy of the 3 WOKVAC doses, will be evaluated by an assessment of the generation of cellular and humoral response to IGFBP-2, HER2, and IGF-1R, development of persistent T cell memory; and modulation of Tregs and MDSC with vaccination as described in Section 13.5.

We will be evaluating the effect of the WOKVAC vaccine on the heart by measuring left ventricular ejection fraction (LVEF) with a MUGA or ECHO before vaccination, one month after the first vaccine, and one month after the vaccination series.

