## 7. CLINICAL EVALUATIONS AND PROCEDURES

### 7.1 Schedule of Events

Evaluation/ Procedure	Baseline 	1 st vaccination	2 nd , 3 rd vaccination 	Post-vaccination Follow-up Visits 	Long-term Follow-up 
Informed Consent	X				
Assess Eligibility	X				
Medical History	X				
Baseline Symptom Assessment	X				
Physical Exam 	X		X	X	
Vital Signs/ and Weight	X	X	X	X	
Concomitant Medications	X	X	X	X	
Assign dose arm	X				
Urine Pregnancy Test 	X	X	X		
CBC 	X	X 	X	X	
CMP 	X	X	X	X	
HbA1c	X			X	
GAD65		X		X	
ANA, anti-dsDNA, C3 and TSH		X	X	X	
Research Blood 		X		X	
Tetanus- diphtheria Immunization 		X			
MUGA/ECHO 	X		X	X	
Symptom Assessment/ Adverse Events		X	X	X	
Dispense Study Vaccine		X	X		
60 minutes post vaccine vitals 		X	X		
Medical Record Chart review					X 

Must occur within 3 weeks (21 days) of 1st vaccination with the exception of CMP, CBC, HbA1c and ECHO/MUGA which must be in acceptable range within 90 days of enrollment

Physical Exam includes: Weight, vital signs, symptom/toxicity assessment, and ECOG scoring

Performed on females who are having sex that could lead to pregnancy.

Complete blood count (CBC) includes differential and platelets.

Complete blood count (CBC) with differential and platelets does not need to be drawn if completed within 90 days of enrollment.

Comprehensive Metabolic Panel (CMP) includes serum electrolytes, creatinine, BUN, AST, ALT, alkaline phosphatase, and total bilirubin. For vaccine visits follow glucose monitoring per section 8.5.1.1.

During the consent process, and at subsequent visits, patients will be instructed to hydrate sufficiently prior to visits requiring large volume blood draws.

Tetanus-diphtheria immunization only given if patient has not received one within 6 months.

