#### 8.5.1. Criteria for Premature Study Termination

Benchmarks for the safety of a dose level will be that there are no attributable (definitely, probably and possibly-related to study drug) grade 4 toxicity and <30% incidence of attributable Grade 3 toxicity (definitely, probably and possibly related to the study agent except as noted in the table below). If the observed rate of each of these toxicities is consistent with these benchmarks, escalation to the next higher dose level will be allowed.

Escalation will not be allowed if the observed toxicity rate exceeds the above. Other participants at the same dose level without toxicities will be allowed to continue at that dose level.

For grade 1 or 2 vaccine-related reactions, patients may be treated with acetaminophen or diphenhydramine as clinically indicated at the discretion of the study clinician and continue to receive vaccinations. For this prevention study  $\geq$  grade 3 attributable toxicity (other than those listed below; CTEP CTCAE v4.0) is considered dose-limiting for the patient. If grade 3 toxicity that is at least possibly related to the vaccine (except as described below) is observed, no further immunizations will be administered to that patient.

If  $\geq 3$  participants experience a grade 3 attributable toxicity, except as noted in the table below, or if any participant experiences a grade 4 attributable toxicity within any dose level, further accrual at that dose level will stop and accrual to the study will be terminated.

Category	Grade 3 Attributable Toxicity/AE	Allowable Duration
General disorders and administration	Flu-like symptoms	1 week
Musculoskeletal and connective tissue disorders	Arthralgia	1 week
	Myalgia	1 week
Investigations	Lymphocyte count decreased	2 weeks
	Platelet count decreased	1 week
	Hemoglobin decrease	1 week
	White blood cells decreased	2 weeks

We would consider a grade 3 or 4 autoimmune event a dose limiting toxicity and would consider steroid administration for grade 3 or 4 adverse immune related events that have been reported with other immune based therapies, i.e. ipilimumab. Examples of such immune related AEs include; rash, diarrhea/colitis, and hepatitis. The following dose schedule may be used:

Day 1-2: Intravenous Solu-Medrol at 1 mg/kg  
Day 3-4: Prednisone at 30 mg BID PO q day  
Day 4-5: Prednisone at 15 mg BID PO q day  
Day 5-6: Prednisone at 10 mg BID PO q day  
Day 6-7: Prednisone at 10 mg PO q day  
Day 8-9: Prednisone at 5 mg PO q day

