### **11.1.2 AE Data Elements:**

The following data elements are required for adverse event reporting:

- CTCAE (MedDRA) System Organ Class (SOC)
- NCI Common Terminology Criteria for Adverse Events v4.0 (CTCAE) AE term (MedDRA lowest level term)
- Event onset date and event ended date
- Severity grade
- Attribution to study agent (relatedness)
- Whether or not the event was reported as a serious adverse event (SAE)
- Whether or not the patient dropped due to the event
- AE verbatim term
- Action
- Outcome
- Treatment assignment code (TAC) at time of AE onset

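### Td reactions are pooled into the vaccine-1 safety profile: adverse events carry one attribution, and no table separates vaccine 1 from vaccines 2 and 3 or Td recipients from the rest

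*Combined protocol and SAP*

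**What the plan says.** **Timing of Td.** The schema lists, for the first vaccination visit, "Tetanus diphtheria (Td) vaccination (if applicable), and intradermal (id) vaccination with assigned dose". Footnote 8 to the Schedule of Events (7.1) adds the condition: "Tetanus-diphtheria immunization only given if patient has not received one within 6 months". Section 7.3.3 provides for "Tetanus diphtheria (Td) immunization if one has not been administered within six months and used as a positive control for immune responses", with one exception: "If patient has a history of an allergic reaction to the Td immunization, one will not be given". Neither 7.1 nor 7.4 schedules Td at vaccines 2 or 3. Sections 5.2 and 7.3.4 say in which limb WOKVAC goes; no section says this for Td.

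**Attribution.** Section 11.1.2 has a single relatedness element ("Attribution to study agent (relatedness"). Section 11.1.4 grades it on five levels, from unrelated to definite. Onset date is among the required elements; Td receipt is not.

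**Early review.** Under Section 3 the first three patients in each arm "receive the first vaccine, and be evaluated for toxicity prior to the second vaccine (1 month of monitoring"), before the rest of the arm is enrolled.

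**Counting rule.** In 8.5.1, definitely, probably and possibly related events all count. At three or more participants with a grade 3 event, or any participant with a grade 4 event, within a dose level, "further accrual at that dose level will stop and accrual to the study will be terminated". A table exempts certain grade 3 events of limited duration, including flu-like symptoms, arthralgia and myalgia lasting up to 1 week.

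**Analysis.** Section 13.4 tabulates all adverse events by body system, gives proportions with 95% confidence intervals, and compares successive dose groups with a nonparametric test. It has no split by vaccine number or by Td receipt.

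**The concern.** Some patients receive two vaccines at the visit that opens the safety record. If such a patient then has a local, systemic or allergic reaction, the design cannot say whether it came from WOKVAC plus GM-CSF or from Td. The adverse event record asks about only one of them.

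The error can go either way. A Td reaction scored as possibly related is counted against WOKVAC. A WOKVAC reaction put down to Td can be coded unlikely or unrelated and leave the attributable count. The Section 13.4 tables include events whatever their attribution, so Td reactions sit in them in either case.

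Safety is the primary endpoint, the arms are small, and vaccine 1 is the only dose that the three-patient review sees. Td receipt depends on each patient's history, and arms are filled in sequence without randomization, so nothing balances it between dose groups.

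**Working it through.** **1. The plan's own figures.** The plan gives no figure for Td. Its one power figure (Section 13.5: effect size 0.281, N = 30, level 0.05, power 0.80) concerns immunogenicity. It reproduces: noncentral F with 1 and 28 df and noncentrality 30 × 0.281 = 8.43 gives 0.8003. This point does not touch it.

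**2. How pooling acts.** For one kind of vaccine-1 event in dose group d, let p_d be the probability that WOKVAC plus GM-CSF causes it, t the probability that Td causes it in a recipient, and s_d the share given Td. If the two causes act independently, the rate tabulated for vaccine 1 is

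p′_d = 1 − (1 − p_d)(1 − s_d·t) = p_d + (1 − p_d)·s_d·t.

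- The rate within an arm is too high by (1 − p_d)·s_d·t, which is above zero whenever some patients get Td and Td can cause the event.
- If two arms have the same true rate p, the tabulated difference is (1 − p)·t·(s_2 − s_1). It is zero when the Td shares are equal.
- If the shares are equal at s, the tabulated difference is (p_2 − p_1)(1 − s·t): slightly shrunk, with no false difference.

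Inflation within arms and bias between arms are therefore separate effects and cannot both be at their largest. With Td given to everyone, the first is at its maximum and a false difference between arms cannot arise.

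**3. Which events reach the 8.5.1 count.** Grade 3 flu-like symptoms, arthralgia and myalgia of up to 1 week are exempt. Section 6.2 describes fever, chills, achiness and fatigue for 1-2 days after earlier vaccines as flu-like symptoms, so much of the likely systemic overlap does not reach the grade 3 count. Local and allergic reactions are not in the exemption table, and grade 4 events have no exemption.

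**4. Why the effect on stopping cannot be sized.** It needs p, t and s for non-exempt grade 3 events; the documents give none of them. The values below are assumptions, used only to show how far the answer moves. The formula is P(X ≥ 3) = 1 − Σ_{k=0}^{2} C(n,k) p′^k (1 − p′)^{n−k}, with n = 10 per arm (13.9).

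| Assumed p | Assumed s | Assumed t | p′ | P(≥3 of 10) |
|---|---|---|---|---|
| 0.05 | – | 0 | 0.050 | 0.0115 |
| 0.05 | 0.5 | 0.01 | 1 − 0.95 × 0.995 = 0.0548 | 0.0147 |
| 0.10 | – | 0 | 0.100 | 0.0702 |
| 0.10 | 1 | 0.05 | 1 − 0.90 × 0.95 = 0.145 | 0.167 |

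The increase is 0.003 in one case and 0.10 in the other, depending only on what is assumed. Neither is evidence about this trial.

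**5. What vaccines 2 and 3 can show.** They are Td-free, so they give a reference within patients. Under 8.5.1, however, a patient with a non-exempt grade 3 event at least possibly related gets no further immunizations. The patients whose vaccine-1 events matter most for stopping are therefore missing from that reference.

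**The case against.** The strongest reply is that the plan already contains most of what is needed. Td is a scheduled procedure, and completion of procedures is tracked (5.7.3). Medications and onset dates are recorded. The attribution scale lets an investigator code a Td reaction as unlikely or unrelated. Vaccines 2 and 3 carry no Td, escalation rests on the whole dose level, and Section 13.4 itself concedes that the dose comparison is non-randomized and insensitive.

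Most of this stands, and it limits the point to recording and tabulation. It does not remove it. No rule says when an event should be put down to Td, a chart entry is not an attribution, and data that could be split are not split in the planned tables.

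A reader might go further in four ways that the documents do not support:

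- *The whole safety assessment is confounded.* Td is conditional and is withheld after a Td allergy. The problem is confined to vaccine-1 events in Td recipients, while the primary endpoint runs to 6 months.
- *Td materially raises the chance of stopping the trial.* This needs rates that the documents do not give, and it overlooks the exemption table.
- *The 200 ml research draw is a further confounder.* It precedes the vaccine, its named effect is lightheadedness or dizziness, and nothing suggests that it produces grade 3 or 4 events.
- *Td should not be given that day, since "there are other positive controls used for immune assays".* That sentence explains why patients with a Td allergy may stay in the study. It does not call Td dispensable, and the choice of control is a design preference.

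**Conclusion.** The point holds in a limited form. For patients who receive Td, the planned tables pool Td reactions with those to WOKVAC plus GM-CSF in the vaccine-1 profile, and the single attribution cannot separate them. Unequal Td receipt would carry into the comparison of successive dose groups; equal receipt would not create a false difference. The effect on the 8.5.1 count is limited by its exemptions but not nil, because local and allergic reactions and all grade 4 events remain countable.

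No size can be given. The conclusion rests on two assumptions: that at least some patients receive Td, and that Td can cause events of the kinds being tabulated. The plan's own provision for Td allergy supports the second. Sample size and power are unaffected. The change is worth making because it improves the primary safety description at little cost.

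**What to change.** - **Sections 11.1.2 and 11.1.4:** record Td receipt with date and limb, and add a separate attribution to Td beside the one to WOKVAC plus GM-CSF. Both can then be scored for the same event.
- **Section 13.4:** tabulate adverse events by vaccine number, and split vaccine-1 events by Td receipt within each dose group. Use vaccines 2 and 3 as the Td-free reference, with a note that patients stopped after a vaccine-1 grade 3 event contribute no later doses. Read the split descriptively, since a first dose may differ from later doses for reasons other than Td.
- **Dose-level reviews (8.5.1, 13.10):** show the count as written, with possibly related events included. Beside it, as a sensitivity display, show the count without events also judged possibly due to Td. The stopping rule itself does not change.

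The cost is slightly more data entry and one more table. Vaccine number follows from onset and vaccination dates, which are already collected.

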7.3.4. WOKVAC vaccine given intradermally

- a. Patients with axillary lymph node dissection (ALND) will have vaccine administered to the contralateral arm. Patients with bilateral ALND will have vaccine administered in the thigh. For 300mcg and 600mcg doses where multiple injections are given, they should each be given in the same area of the arm or leg.
- b. Vaccines will be administered in the outpatient setting at the UW CRC or at the UWI CRU.
- c. 60 minutes post vaccine observation including vital signs (collection between 55-75 minutes post vaccination is allowed) (see section 6.2)

#### **7.4 Second and Third Vaccination**

7.4.1. Clinical labs prior (within 2 days of visit is allowable):

- a. CBC
- b. CMP
  - i. Review non-fasting glucose value prior to vaccine administration then follow Section 8.5.1.1 to determine whether vaccine can be administered.
- c. ANA, C3, anti-dsDNA, TSH

7.4.2. MUGA or ECHO prior to the second vaccine only (within 1 week of the scheduled visit)

- a. LVEF must be  $\geq$ LLN per institution performing the test, to allow the patient to continue with vaccination
- b. The same monitoring modality used at baseline must be used

7.4.3. A physical examination will be done that will include weight, vital signs, symptom/toxicity assessment, and ECOG scoring.

7.4.4. Urine Pregnancy Test if applicable

7.4.5. Vaccines may be scheduled every 28 (+7) days from previous vaccine.

- a. Vaccines will be administered i.d. (see 7.3.4.a). As much as possible each vaccine dose should be given in the same area of the arm or leg as the first vaccine.
- b. Vaccines will be administered in the outpatient setting at the UW CRC or at the UWI CRU
- c. 60 minutes post vaccine observation including vital signs (collection between 55-75

minutes post vaccination is allowed)  
i. See 6.2 regarding allergic reactions

### **7.5 Evaluation at Completion of Study Intervention**

(The 1-month post vaccine visit must occur 28(+7) days following the last vaccine. The 6-month post vaccine visit must occur 168 ( $\pm 14$ ) days following the last vaccine.)

- 7.5.1. MUGA or ECHO (completed at 1-month post vaccine visit) using the same imaging modality used at baseline
- 7.5.2. A physical examination will be performed which will include weight, vital signs, symptom/toxicity assessment and ECOG scoring.
  - a. Clinical labs:
  - b. CBC
  - c. CMP
  - d. ANA, C3, anti-dsDNA, TSH
  - e. HbA1c and GAD65

7.5.3. Research blood:

Approximately 200mls of blood will be collected for immunologic monitoring. It is possible that this volume of blood loss could cause the patient to feel lightheaded or dizzy. If clinically indicated, IV fluids will be administered.

### **7.6 Long-Term Follow-up (LTFU) Period**

- 7.6.1. Information on patient's health status will be requested from the patient's primary oncologist or primary care physician annually from enrollment to complete 5 years. The following will be requested and reviewed:
  - a. Clinical notes
  - b. Laboratory values
  - c. Imaging reports

Notes will be reviewed by study team for vaccine toxicity such as site reaction and possible autoimmune symptoms (examples - unexplained rash, dry eyes, unexplained diarrhea) and overall relevant health status within the above collected records.

### **7.7 Methods for Clinical Procedures**

Although patients have a small chance of experiencing an allergic-type reaction to the vaccine, if a reaction were to happen, it would usually occur within one hour of the vaccination. For this reason, all patients will undergo observation for a minimum of 60 minutes post-vaccination, after which time vital signs will be performed.

Large volume blood draws (up to 200mls) are required at designated study visits for immunologic monitoring. The amount of blood obtained for immunologic monitoring assays is in strict adherence with guidelines set by the Puget Sound Blood Center and are associated with minimal risks. However, as with any large volume blood draw patients should be well hydrated prior to the draw. Thus, during the consent process, and at subsequent visits, patients will be instructed to hydrate sufficiently prior to visits requiring large volume blood draws. If it is clinically indicated, IV fluids will be administered.

